### Non-Erythematous Skin Discoloration

This finding has been noted infrequently in studies of the system. Following an initially erythematous rash, the skin can take on a brownish hue in the areas of prior erythema. This should not be considered a new skin AE, as it is a continuation of the previous AE. If detected, the investigator should list “non-erythematous skin discoloration” as a new skin finding in the associated data field. On each subsequent assessment, the investigator must make the determination of “resolved,” “resolving,” “unresolved,” or “resolved with sequelae.”

## **8.0 CRITERIA FOR DISCONTINUATION**

### 8.1 Criteria for Treatment Discontinuation

- Drug-related toxicity (see Section 7.2, Toxicity Management).
- Requirement for prohibited concomitant medications (see Section 5.5.2)

### 8.2 Criteria for Discontinuation from the Study

- Pregnancy or breast-feeding.
- Active drug or alcohol use or dependence that, in the opinion of the investigator, would interfere with adherence to study requirements.
- Failure by the subject to attend three consecutive clinic visits during the follow-up portion may result in discontinuation.
- Request by the subject to withdraw.

- Request of the primary care provider if s/he thinks the study is no longer in the best interest of the subject.
- Clinical reasons believed life threatening by the physician, even if not addressed in the toxicity management of the protocol.
- Subject judged by the investigator to be at significant risk of failing to comply with the provisions of the protocol as to cause harm to self or seriously interfere with the validity of the study results.
- At the discretion of the AVRC, investigator, or sponsors.

## 9.0 STATISTICAL CONSIDERATIONS

### 9.1 General Design Issues

This study is a prospective, two phase, open-label feasibility study with lead in (Phase 1) and randomized (Phase 2) components to evaluate the utility of the DHFS for monitoring TB treatment. In the first phase, all subjects will receive DHFS IS-RM (or Rifamate with co-ingestion of an encapsulated edible sensor) and a series of doses will be witnessed in order to determine the detection accuracy of the system as well as to evaluate subject acceptance and ability to use the system. In the randomized phase, those randomized to intervention will continue to use the DHFS IS-RM and control subjects will receive SOC DOT.

### 9.2 Endpoints

#### 9.2.1 Primary Endpoints

##### Phase 1 (1.2.1) Positive Detection Accuracy (PDA)

PDA is defined as DHFS detection of the ingestion of a dose of IS-RM (or Rifamate with co-ingestion of an encapsulated edible sensor) when compared to a witnessed ingestion of the same dose of medication. For purposes of PDA analysis, a dose is defined as a single IS-RM capsule. PDA will be based upon dose ingestions that occur during concurrent use of DHFS and DOT during the planned Phase 1 study visits. A minimum of 280 dose ingestions are required to generate sensitivity and specificity of the System.

##### Phase 2 (1.2.2) Percentage of Witnessed Doses

This will be calculated as the total number of witnessed doses ingestions divided by the total number of prescribed witnessed dose ingestions. For the DHFS, witnessed doses by DHFS is defined as the total number of dose ingestions confirmed by DHFS, divided by the total number of prescribed witnessed dose ingestions for TB treatment. For SOC, witnessed doses will be defined as the total number of dose ingestions that are actually witnessed by a healthcare worker, divided by the total number of prescribed witnessed dose ingestions for TB treatment. This endpoint will be calculated from Phase 2, Day 0 to Weeks 4, 8 and end of study.

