Per CDC guidelines, DOT can take place five, three, or two times per week, with the medication dose adjusted to the frequency of medication taking. Although DOT is the gold standard for monitoring therapy, it can be difficult to execute perfectly, since subjects may miss DOT appointments for vacation, work, or other reasons, and conversely DOT workers may miss appointments due to overscheduling or transportation failure. Thus, the adherence metrics chosen for this study need to carefully take into account the unique nature of DOT, as adherence determined by the number of witnessed doses ingested. The optimal adherence metric for this study is the total number of actual witnessed dose ingestions divided by the total number of prescribed witnessed dose ingestions, captured by DOT or via DHFS. This parameter, the percentage of witnessed doses, will be reported for the duration of the study (per week, per month and over the entire study period). The percentage of witnessed doses in this trial captures effective monitoring of TB treatment via DOT and DHFS, and allows calculation of adherence with SOC DOT at varying intervals, e.g., five, three, or two times per week.

TB treatment has largely grown up through convention and analysis of treatment failures in traditional clinical practice, rather than extensive clinical trials with pharmacokinetic and therapeutic drug monitoring. Thus patterns of drug administration given via DOT five, three, or two times per week have been deemed acceptable based on treatment failure rates, with adherence  $\geq 80\%$  of prescribed dosing estimated by key opinion leaders as adequate for TB treatment [21]. Daily DOT may give more favorable pharmacokinetic profiles for isoniazid and rifampin with their relatively short half-lives (isoniazid-1.5 hours [fast acetylators] to 4 hours [slow acetylators]; rifampin-3 hours). Random and sparse sampling of therapeutic drug concentrations may confirm adherence monitoring data obtained via DHFS and SOC DOT; and pharmacokinetic evaluation of daily and five, three, and two times weekly dose administration may be analyzed. Stored plasma samples in this trial may allow future pharmacokinetic analysis with random sampled dosing history data providing the foundation for sound pharmacological interpretation of dose- or exposure-dependent variations in drug response in ambulatory care of TB.

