## 9.4 Sample Size and Accrual

Phase 1: For phase 1, both groups will use the DHFS for 2 weeks, and we will estimate the confidence interval around an estimate of the detection accuracy of the DHFS by taking the ratio of the sensor-enabled ingestion recorded events compared to the witnessed doses. Assuming that each of 75 subjects completes 2 weeks of DHFS dosing and has a total of three witnessed doses each week (a total of 450 dosing events) and that the overall rate of positive detection is 95%, then the 95% confidence interval around the point estimate of 95% accurate detection would be  $\pm 2.0\%$ . If the detection accuracy was 97%, then the 95% confidence interval around the point estimate of 97% accurate detection would be  $\pm 1.6\%$ .

Phase 2: The primary aim of phase 2 is to assess the percentage of prescribed witnessed doses completed over the entire study period for each subject and to compare the DHFS arm to the DOT arm. This metric captures the persistent efficacy of the DHFS ingestion sensor system and allows comparison to SOC DOT of varying intervals (5 times, 3 times, or 2 times per week that may occur in the SOC). Sample size calculations were based on a two-sided, two-sample t-test to compare the differences in adherence percentages by treatment arm using different mean/standard deviation scenarios. Calculations were performed using the R statistical package (version 2.14.0) ([www.r-project.org](http://www.r-project.org)).

In choosing a sample size for this pilot study, we considered issues of cost, feasibility, as well as how large an effect size would be of interest to spur further study of this intervention in this population. Assuming a two-sided alpha of 0.05, an adherence percentage in the DOT arm of 90%, and a common standard deviation of 6%, we will need 75 participants (50 DHFS arm and 25 DOT arm) to detect a 5% difference (i.e. 95% adherence percentage in DHFS arm) with 92% power.

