#### Phase 2 (Percentage of Witnessed Doses)

A mixed effects regression model will be used to determine if the WOT intervention arm will produce greater percentage of witnessed doses compared to the DOT standard of care arm at treatment end. This model will include time, treatment arm, and time-by-treatment arm interaction terms. In addition, any covariates, which are simultaneously unbalanced at baseline and associated with the outcome, will be included in the model. Time will be treated as a categorical variable. A significant treatment effect will be concluded if the p-value for the time-by-treatment interaction contrast in the model is  $\leq 0.05$ . Permutation tests may be implemented to verify that valid p-values will be obtained even if model assumptions are not correct. Note that the linear mixed model seamlessly accommodates different times of measurement as well as missed measurements and data from subjects who are lost to follow-up. Generalized estimating equation (GEE) models will be used as the sensitivity analysis method.

Note that when considering percentages of witnessed doses over the entire study period in aggregate, this model reduces to a multiple linear regression, and the independent variable of interest is the treatment arm.

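### The Phase 2 primary test (a mixed model on overlapping cumulative percentages, judged on an interaction contrast) is not the test that the 92% power was calculated for

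*Combined protocol and SAP*

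**What the plan says.** Section 9.2.1 defines the Phase 2 endpoint as witnessed doses divided by prescribed witnessed doses, and adds: "This endpoint will be calculated from Phase 2, Day 0 to Weeks 4, 8 and end of study". Section 3.6 has a similar sentence. Each window starts at Day 0, so the Week 8 value contains the Week 4 doses and the end value contains both. Section 3.5 allows a Phase 2 of only four weeks, in which case a subject's Week 4 and end values are the same number.

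Section 9.6.1 plans a mixed model with time, arm and their interaction, aimed at treatment end. It says "Time will be treated as a categorical variable" and concludes a treatment effect if the p-value of the time-by-treatment interaction contrast is at most 0.05. It states neither the covariance structure nor which time points form the contrast. It names GEE as the sensitivity analysis and allows permutation tests. It also notes that, for the whole period in aggregate, the model reduces to multiple linear regression on arm.

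Section 9.4 powers a different analysis: "Sample size calculations were based on a two-sided, two-sample t-test to compare the differences in adherence percentages by treatment arm". The quantity is each subject's percentage over the entire study period. The inputs are "an adherence percentage in the DOT arm of 90%, and a common standard deviation of 6"%, and the result is that "we will need 75 participants (50 DHFS arm and 25 DOT arm) to detect a 5% difference", with 92% power.

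**The concern.** The test that decides the trial differs from the test that was powered, and the text leaves its behaviour open in two ways.

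First, nested cumulative percentages need not have equal variances at Week 4, Week 8 and end of study. A random-intercept model, a common default, assumes that they do, and carries the average of the three variances into the contrast at treatment end. The standard error can then be too large or too small, depending on how the spread changes over time.

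Second, an interaction contrast compares arm differences between time points. That is not the arm difference at treatment end. If the arms differ by the same amount throughout, the interaction is zero however large the benefit.

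At stake are the false-positive rate and the power of the only randomised primary comparison.

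**Working it through.** **Inputs from section 9.4:** two-sided alpha 0.05, difference 5 points, SD 6 for the whole-period percentage, 25 DOT and 50 DHFS. The documents give no SD for Week 4 or Week 8, so the patterns below are assumptions.

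**1. The plan's own figure.** SE = 6 × √(1/25 + 1/50) = 6 × 0.2449 = 1.470. Power = Φ(5/1.470 − 1.96) = Φ(1.442) = 92.5%. The noncentral t with 73 df gives 91.9%. The stated 92% is right for one value per subject.

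**2. Arm difference at treatment end from the mixed model.** With complete data and a full time-by-arm model, the estimate at end is the raw difference in means, with true SE 1.470 if the end SD is 6. A random-intercept model reports

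SE_model = √[(s₄² + s₈² + s_end²)/3] × 0.2449.

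Null rejection is 2[1 − Φ(1.96 × SE_model/1.470)]. Power is Φ[(5 − 1.96 × SE_model)/1.470].

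For falling SDs, let a share f of the end variance be week-to-week noise that averages out, with end at week T. The variance at week t is then 36(1 − f) + 36·f·T/t. For T = 24 and f = 0.25, Week 4 gives 27 + 9 × 24/4 = 81, so the SD is 9.0.

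| Assumed SDs (Week 4 / Week 8 / end) | SE_model | Null rejection | Power |
|---|---|---|---|
| 7.35 / 6.57 / 6 (T = 24, f = 0.10) | 1.63 | about 3% | 89% |
| 9.0 / 7.35 / 6 (T = 24, f = 0.25) | 1.85 | 1.4% | 82% |
| 11.2 / 8.5 / 6 (T = 24, f = 0.50) | 2.16 | 0.4% | 70% |
| 6 / 6 / 6 | 1.47 | 5% | 92.5% |
| 4 / 5 / 6 | 1.24 | 9.8% | test not valid |
| 3 / 4 / 6 | 1.10 | 14.1% | test not valid |
| any of these, unstructured covariance | 1.47 | about 5% | about 92% |

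With T = 12 and the same three shares, power is 91%, 89% and 86%. Fitted random-intercept models on simulated data agree for T = 24 (88%, 84%, 71%).

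**3. Dose-level simulation.** Assumptions: 50 v 25 subjects, beta-distributed subject rates with between-subject SD 5%, binomial doses, daily DHFS, DOT two, three or five times a week, Phase 2 up to 24 or 50 weeks, common-variance model. Null rejection for the end contrast is 2% to 3%. Power at 95% v 90% is 86% to 89%, against 90% to 94% for Welch's test on one whole-period value: a loss of about 4 to 5 points. The equal-variance t-test is not a fair comparator. It rejects about 6% under the null, because the smaller DOT arm has fewer doses per subject and so the larger variance.

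**4. The decision rule read as end minus Week 4.** If the difference is 5 points from Day 0, every cumulative difference is 5 and the contrast is 5 − 5 = 0. Under the weekly-noise pattern, the random-intercept model reports 2/3 of the contrast's true variance, so its SE is √(2/3) = 0.816 of the true SE. Null rejection is 2[1 − Φ(1.96 × 0.816)] = 2[1 − Φ(1.600)] = 11%. In the dose-level simulation it is about 17%, and a constant 5-point difference is declared significant only about 20% of the time. With an unstructured covariance both rates are about 5%.

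**The case against.** Section 9.6.1 does not say that the three cumulative values are the model's input. Section 2.2 says the percentage "will be reported for the duration of the study (per week, per month and over the entire study period"), and weekly or monthly values need not overlap. Section 9.6 calls itself brief and defers to an SAP, to be finalised before database lock, which takes precedence; no separate SAP text is available here. The phrase about treatment end suggests that the end-of-treatment difference is intended. GEE and permutation tests offer some protection, and the aggregate regression is already mentioned.

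Much of this stands. The model's input is an inference, though Weeks 4, 8 and end are the only time points that section 9.2.1 gives the endpoint. A missing covariance line does not show that none is planned. But the safeguards do not change the primary test: permutation is optional, GEE is a sensitivity analysis, and the regression is a note. Neither GEE nor permutation turns an interaction contrast into the arm difference at end.

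A reader might infer that overlap by itself makes the standard error too large and costs power. The documents do not support that. It takes both a common-variance model and SDs that fall over time, and neither is stated. The same overlapping windows with an unstructured covariance keep about 92%, and growing spread reverses the direction.

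A reader might also argue that cumulative values hide late decline, so the primary endpoint should change. The whole-period percentage shares that property, so this argument supports only non-overlapping intervals for the time course.

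**Conclusion.** The concern holds in this form: the primary test in section 9.6.1 is not the one powered in section 9.4, and its error rate rests on choices the plan does not state.

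No single figure for lost power can be derived, because only the whole-period SD is given. Under the assumptions in the working, the end-of-treatment test ranges from conservative (a loss of about 4 to 5 points in the dose-level scenarios) through correct (unstructured covariance) to anti-conservative (10% to 14% false positives in the two growing-spread examples).

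The larger risk is the literal interaction contrast, which is zero for a difference that is constant from Day 0. That result needs no assumption about covariance, only that the contrast compares end of study with an earlier window. All the patterns assume that the cumulative values are the model's input; the calculations in steps 1 and 2 also assume complete, roughly normal data. The rule should be settled before the SAP is finalised.

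**What to change.** 1. Define the primary Phase 2 analysis as the arm difference in the whole Phase 2 percentage, one value per subject. Use the linear regression already named in section 9.6.1 with heteroscedasticity-consistent standard errors, because DOT subjects have fewer prescribed doses and the arm variances are likely to differ. Replace the interaction-contrast rule with the p-value for arm from this regression. The primary test then targets the quantity powered in section 9.4.
2. Keep the mixed model as a supporting time-course analysis on non-overlapping intervals (Weeks 0 to 4, 5 to 8, then every four weeks, in line with the monthly reporting in section 2.2), with an unstructured or robust covariance. State the input values and each contrast. Intervals that do not overlap will also show late decline.

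The cost is wording in section 9.6.1 and the SAP. The data and the sample size are unchanged.

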## 9.3 Randomization

Subjects will be randomized 2:1 to DHFS or SOC. Randomization will be done centrally via the study database.

## 9.4 Sample Size and Accrual

Phase 1: For phase 1, both groups will use the DHFS for 2 weeks, and we will estimate the confidence interval around an estimate of the detection accuracy of the DHFS by taking the ratio of the sensor-enabled ingestion recorded events compared to the witnessed doses. Assuming that each of 75 subjects completes 2 weeks of DHFS dosing and has a total of three witnessed doses each week (a total of 450 dosing events) and that the overall rate of positive detection is 95%, then the 95% confidence interval around the point estimate of 95% accurate detection would be  $\pm 2.0\%$ . If the detection accuracy was 97%, then the 95% confidence interval around the point estimate of 97% accurate detection would be  $\pm 1.6\%$ .

Phase 2: The primary aim of phase 2 is to assess the percentage of prescribed witnessed doses completed over the entire study period for each subject and to compare the DHFS arm to the DOT arm. This metric captures the persistent efficacy of the DHFS ingestion sensor system and allows comparison to SOC DOT of varying intervals (5 times, 3 times, or 2 times per week that may occur in the SOC). Sample size calculations were based on a two-sided, two-sample t-test to compare the differences in adherence percentages by treatment arm using different mean/standard deviation scenarios. Calculations were performed using the R statistical package (version 2.14.0) ([www.r-project.org](http://www.r-project.org)).

In choosing a sample size for this pilot study, we considered issues of cost, feasibility, as well as how large an effect size would be of interest to spur further study of this intervention in this population. Assuming a two-sided alpha of 0.05, an adherence percentage in the DOT arm of 90%, and a common standard deviation of 6%, we will need 75 participants (50 DHFS arm and 25 DOT arm) to detect a 5% difference (i.e. 95% adherence percentage in DHFS arm) with 92% power.

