### 3.5 Study Design

Phase 1: A two-week period where the subjects receive DHFS IS-RM (or Rifamate with co-ingestion of an encapsulated edible sensor), in conjunction with witnessed medication doses to determine the positive detection accuracy and characteristics of use of DHFS in the TB patient population.

Phase 2: A period of TB treatment monitoring randomized to DHFS IS-RM or SOC DOT, for a minimum of 4 weeks and continuing until completion of TB treatment (up to a maximum of 12 months on study).

These study periods are designed to capture the following information. Phase 1 will gather information on the verification of DHFS ability to capture medication ingestion events alongside simultaneous witnessed ingestions. This Phase incorporates DHFS use at the AVRC or OCHCA clinic with simultaneous witnessed ingestions by clinic staff to ascertain the positive detection accuracy (with calculation of sensitivity and specificity), system function, and the subject's ability to interface with the DHFS system as currently designed. Phase 2 represents a period of persistence with DHFS IS-RM or SOC DOT and monitoring of patient medication taking behavior until the completion of TB consolidation treatment or termination on the study.

In Phase 1 (Weeks 0-2), all subjects will use DHFS and receive the study drug in conjunction with DOT. The wearable sensor will be changed weekly (or earlier if needed) by the subject themselves under the supervision of study personnel. Subjects will be required to visit the AVRC two times a week during this phase to complete DHFS/DOT doses. In the case of Orange County participants, AVRC personnel will conduct all study visits at the OCHCA clinic. County outreach workers will also provide at least three visits per week during Phase 1, providing a combined minimum of five days of DOT per week in conjunction with study drug ingestion. Upon completion of four successful ingestions of Rifamate with concurrent use of DHFS and witnessed DOT during study visits, and two successful patch changes performed under

observation by study personnel, Phase 1 of the study will be completed. The first patch change may include minimal coaching, but no intervention by study personnel. The second patch change must occur without any coaching or intervention by study personnel. Subjects deemed eligible by study personnel and who wish to continue will be randomized and proceed to Phase 2.

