#### 9.6 Analyses

This section briefly describes the planned statistical analysis. The Statistical Analysis Plan (SAP), which will be finalized prior to database lock, provides further details. In case the language in this section differs from the language in the SAP, the SAP takes precedence.

In general, analyses will incorporate the modified intent-to-treat principle, namely, all randomized participants dispensed at least one dose of medication will be included in the analysis. No adjustments for multiple comparisons will be made for secondary analyses, and a p-value of 0.05 will be considered statistically significant.

Demographic data, concomitant medications, site of TB infection, adverse events prior to entry into study due to TB medications and past medical history will be collated and described for all study subjects and presented in aggregate for phase 1 and by randomized group for phase 2.

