### 9.6.1 Analysis for Primary Outcomes

#### Phase 1 (Detection Accuracy of the DHFS)

The primary analysis of the positive detection accuracy will be done by calculating the number of correct sensor detected IS-RM (or Rifamate with co-ingestion of an encapsulated edible sensor) ingestions divided by the total number of actual witnessed ingestion events with a 95% confidence interval. The data will be reviewed to detect false positive events (recorded ingestion when none should have occurred), especially on days where an observed dose is given and ingestion was recorded at another time. False positive and false negative ingestions will be determined as well as true positive ingestions. An intent-to-treat (all inclusive analysis) will be done that includes all events but will exclude doses that were either known to be not ingested or ingested during the period of time when the patch was known not to be worn. An additional adjusted analysis will use the same definition, but will exclude doses that were taken during a time period when the patch was not functioning properly, either by malfunction or user error.

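### The Phase 1 precision in Section 9.4 assumes independent ingestions, Section 9.6.1 names no within-subject interval for PDA, and the 450-event count is not reconciled with the endpoint

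*Combined protocol and SAP*

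**What the plan says.** Section 9.4 takes 75 subjects over two weeks, each of whom "has a total of three witnessed doses each week (a total of 450 dosing events"), and gives half-widths of 2.0 points at 95% detection and 1.6 points at 97%.

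Section 9.6.1 (Phase 1) defines the analysis as correct sensor detections "divided by the total number of actual witnessed ingestion events with a 95% confidence interval". It names neither the type of interval nor any allowance for repeats. Its all-inclusive analysis leaves out doses known not to have been swallowed and doses "ingested during the period of time when the patch was known not to be worn". Doses taken while a patch malfunctioned or was misused leave only in the adjusted analysis. The methods for repeated data belong to Phase 2: a mixed model, and then "Generalized estimating equation (GEE) models will be used as the sensitivity analysis method". Section 9.6 defers detail to a separate plan: "In case the language in this section differs from the language in the SAP, the SAP takes precedence".

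On the unit, Section 9.2.1 says "For purposes of PDA analysis, a dose is defined as a single IS-RM capsule" and "PDA will be based upon dose ingestions that occur during concurrent use of DHFS and DOT during the planned Phase 1 study visits". Section 3.5 says "Subjects will be required to visit the AVRC two times a week during this phase to complete DHFS/DOT doses", and Section 6.2.1.4 agrees on two study visits a week. Section 3.6 expects two capsules daily.

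**The concern.** A binomial interval on a pooled count is valid when each ingestion is a separate draw. Here one subject contributes several. The patch is changed about weekly, so successive doses can share a patch. The same person handles the system throughout, and two capsules taken together meet the same patch at the same moment. Section 9.6.1 itself recognises patch malfunction and user error as reasons for a missed detection and keeps both in the all-inclusive analysis. If misses cluster in this way, 450 events carry less information than 450 independent ones, and an interval labelled 95% covers less than 95%.

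PDA is the Phase 1 primary endpoint, so at stake is the stated certainty about detection accuracy. A second, separate issue is that planned precision should refer to the unit and number of events that will be analysed.

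**Working it through.** **Inputs.** 75 subjects, 450 events, detection 95% and 97% (9.4); enrolment 75–100 (Schema); single capsule as unit, planned study visits only (9.2.1); two study visits a week for two weeks (3.5, 6.2.1.4); two capsules daily (3.6); 99.4% sensitivity in earlier testing of the latest configuration (2.2). The ICC is not given; 0 to 0.3 is an assumption.

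**Step 1: reproduce 9.4.** 1.96 × √(p(1−p)/450):
- p = 0.95: 1.96 × √(0.0475/450) = 2.01 points
- p = 0.97: 1.96 × √(0.0291/450) = 1.58 points

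Both round to the stated figures, so the within-subject correlation was taken as zero.

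**Step 2: count the events.** 9.4 uses 75 × 3 × 2 = 450. The other sections allow several totals:
- Four study visits, two capsules each: 75 × 4 × 2 = 600. The witnessed-dose row of Table 1 also marks four Phase 1 visits.
- Section 3.5 omits final-day detections from the retrieved log. If that removes the fourth visit: 75 × 3 × 2 = 450, but split four capsules then two by week, not three each week. Section 9.6.1 states no matching exclusion from the denominator.
- Sections 3.5, 3.5.3 and 9.2.1 allow Rifamate with a co-ingested encapsulated sensor, worded in the singular and with no number per dose. With one sensor per visit: 75 × 4 = 300.

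A Table 1 footnote mentions three visits for witnessed doses, but its marker sits on another row and it does not say whether this is per week or in total. Three a week also equals the minimum number of county outreach visits in 3.5, which are additional to the study visits.

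**Step 3: allow for clustering.** Half-width = 1.96 × √(p(1−p) × D/(k·m)), with D = 1 + (m−1) × ICC, k subjects and m events each. Results in points, PDA 95%/97%, k = 75:

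| Events per subject (total) | ICC 0 | ICC 0.05 | ICC 0.1 | ICC 0.3 |
|---|---|---|---|---|
| 8 (600) | 1.74/1.36 | 2.03/1.59 | 2.27/1.78 | 3.07/2.40 |
| 6 (450) | 2.01/1.58 | 2.25/1.76 | 2.47/1.93 | 3.18/2.49 |
| 4 (300) | 2.47/1.93 | 2.64/2.07 | 2.81/2.20 | 3.40/2.66 |

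Example, m = 8 and ICC 0.1: D = 1 + 7 × 0.1 = 1.7; 1.96 × √(0.0475 × 1.7/600) = 2.27.

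**Step 4: where the stated precision still holds.** Break-even ICC = (k·m/450 − 1)/(m − 1):
- 75 subjects, 8 capsules: (600/450 − 1)/7 = 0.048
- 75 subjects, 6 events: 0
- 100 subjects, 8 capsules: (800/450 − 1)/7 = 0.111
- 100 subjects, 6 events: (600/450 − 1)/5 = 0.067
- 4 events per subject: none, since 300 or 400 events is already below 450

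At PDA 99.4% with 75 subjects the half-width is 0.62 (8 capsules, ICC 0) to 1.2 points (4 events, ICC 0.3).

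**Step 5: coverage.** In a beta-binomial simulation (40,000 runs per cell; 75 subjects, 8 capsules), a pooled Wilson interval that ignores clustering covered, at ICC 0/0.05/0.1/0.3:
- PDA 95%: 95/91/87/74%
- PDA 97%: 96/92/89/76%
- PDA 99.4%: 97/95/93/87%

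**The case against.** Several points on the other side stand.

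- The sums in 9.4 are correct. A reader might infer an arithmetic error; there is none. The issue is an unstated assumption.
- A reader might infer that the trial will report a naive interval. The documents do not say so. Section 9.6.1 is a brief description, and the SAP, which prevails, was not available and may name a clustered method. Under-coverage therefore depends on a naive interval being used and on a non-trivial ICC. What survives is that 9.4's own stated precision already assumes independence, whatever the SAP says.
- A reader might take 600 as the true count, or take the mismatch as proof that the interval is too narrow. Neither follows. The final-day exception can return 450 and the co-ingested sensor could give 300. With independent events, 600 gives a narrower interval than stated and 300 a wider one.
- The ICC range has no source in the documents, and the lowest coverage, 74%, lies at its top. With 100 subjects and 8 capsules, ICC 0.1 still gives 1.97/1.54, within the stated figures.
- This is a pilot. No threshold or test uses the PDA interval, and the 75 randomised subjects are justified by the Phase 2 power calculation.

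**Conclusion.** The point holds as one of precision and analysis method, at low to moderate severity. The figures of 2.0 and 1.6 points are right only for 450 independent events, and the visible plan does not say how the PDA interval will handle repeats within subject. With 75 subjects and an assumed ICC of 0 to 0.3, the half-width at 95% detection lies between 1.7 and 3.4 points across the three readings of the count, and at 97% between 1.4 and 2.7. The loss is modest if detection is near 99.4%, and absent at 100 subjects with 8 capsules up to an ICC of about 0.11.

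Separately, the unit and count in 9.4 are not reconciled with Sections 9.2.1, 3.5, 3.5.3, 3.6, 6.2.1.4 and Table 1. The consequence is overstated certainty and a planned precision tied to an unclear unit; no decision in the protocol turns on it.

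**What to change.** **In 9.6.1 and the SAP:** state that, for both the all-inclusive and the adjusted analysis, the PDA 95% interval treats the subject as the cluster, using a method that stays defined near 100% detection, with a pre-specified fallback if nothing is missed. One example is a Wilson interval on the effective sample size (events divided by the subject-clustered design effect, not below 1), with a planning design effect used if every ingestion is detected. Other methods meeting these conditions would serve.

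**In 9.4:** state the unit, the visits per subject and the sensors per visit, reconciled with the sections above. Treat the final-day ingestion the same way in numerator and denominator. Restate precision over an assumed ICC range, as in the table.

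**Cost:** wording, a little more analysis work and possibly a slightly wider stated precision. No new patients and no new data.
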